12.5. Appendix 5: Contraceptive Guidance and Collection of Pregnancy Information

Contraception Guidance

Male participants

- Male participants with female partners of child-bearing potential are eligible to participate if they agree to ONE of the following during the protocol-defined time frame in Section 6.1:
 - Are abstinent from penile-vaginal intercourse as their usual and preferred lifestyle (abstinent on a long term and persistent basis) and agree to remain abstinent
 - Agree to use a male condom plus an additional method of contraception with a failure rate of <1% per year when having penile-vaginal intercourse with a woman of childbearing potential
- Men with a pregnant or breastfeeding partner must agree to remain abstinent from penile-vaginal intercourse or use a male condom during each episode of penile penetration during the protocol-defined time frame.
- In addition, male participants must refrain from donating sperm from session 2 to end of final study follow-up.

Collection of Pregnancy Information

Male participants with partners who become pregnant

- Investigator will attempt to collect pregnancy information on any male participant's female partner of a male study participant who becomes pregnant while participating in this study. This applies only to participants who receive study treatment.
- After obtaining the necessary signed informed consent from the pregnant female partner directly, the investigator will record pregnancy information on the appropriate form and submit it to GSK within 24 hours of learning of the partner's pregnancy.
- Partner will also be followed to determine the outcome of the pregnancy. Information on the status of the mother and child will be forwarded to GSK
- Generally, follow-up will be no longer than 6 to 8 weeks following the estimated delivery date. Any termination of the pregnancy will be reported regardless of foetal status (presence or absence of anomalies) or indication for procedure.

**Description:**

- This version of the RAP is intended to describe the safety and biomarker analyses required for dose escalation and planned biomarker analyses required for interim analyses for study 207654. A subsequent version of the RAP will be developed for Final study reporting.
- Only sections related to dose escalation and interim analyses have been described.

## 1. INTRODUCTION

The purpose of this reporting and analysis plan (RAP) is to describe the safety and biomarker analyses required for dose escalations and planned biomarker analyses required for interim analyses for Protocol:

Revision Chronology:		
2016N309726_00	08-May-2017	Original
2016N309726_01	07-AUG-2017	Change of GM-CSF (LEUKINE) administration from subcutaneous to IV infusion. This is due to liquid LEUKINE no longer being available from the manufacturer Sanofi-Aventis, however lyophilised LEUKINE is available. The guidelines for reconstitution of lyophilised LEUKINE prevent us from administering by subcutaneous as the volume would be too high. In order to remain consistent with clinical practice in dosing GM-CSF therapeutically the dose will be calculated using body surface area.

## 2. SUMMARY OF KEY PROTOCOL INFORMATION

### 2.1. Changes to the Protocol Defined Statistical Analysis Plan

Changes or deviations to the originally planned statistical analysis specified in the protocol (Dated: 08-May-2017) and protocol amendment 1 (Dated: 07-Aug-2017) are outlined in [Table 1](#) for this version of the RAP.

**Table 1 Changes to Protocol Defined Analysis Plan**

[figure not shown]
Protocol	Reporting & Analysis Plan	
Statistical Considerations	Statistical Analysis Plan	Rationale for Changes

 
Sample size re-estimation will be conducted following Part I of the study.
 
	
 
Sample size re-estimation will not be conducted
 
	
 
The methodology used for the original sample size calculation is no longer applicable, therefore the sample size re-estimation will not be conducted. Instead a set of criteria outlined in Section 3.2 will be used to decide if additional participants will be enrolled in Part II of the study.
 

 
Randomized Population (All participants who are randomized to receive and are given the treatment (LPS or GM-CSF challenge)) is defined as one of the analysis population.
 
	
 
Randomized Population will not be used for Analysis
 
	
 
The randomized and safety populations have the same definitions. Hence only safety population would be used.
 

## 2.2. Study Objective(s) and Endpoint(s)

Objectives	Endpoints
Primary Objectives	Primary Endpoints

 
To compare and define the time course of soluble and cellular inflammatory biomarkers (and urinary prostaglandins for LPS only) following systemic challenge with LPS or GM-CSF in healthy participants
 
	
 
For LPS only: time course and magnitude of upregulation of circulating TNF-<math>\alpha</math> and IL-6 as well as urinary tetranor PGDM
 
For GM-CSF only: time course and magnitude of upregulation of circulating total leukocyte numbers.
 

Secondary Objectives	Secondary Endpoints

 
To compare soluble and cellular inflammatory biomarkers in cantharidin-induced skin blisters at baseline versus systemic challenge with LPS or GM-CSF in healthy participants
 
	
 
Soluble inflammatory biomarkers in skin blisters (may include but not limited to IL-1b, IL-2, IL-6, IL-8, IFN<math>\gamma</math>, TNF-<math>\alpha</math>, MCP-1, GM-CSF, CRP).
 
Blister volumes and differential cell counts (cellular activation markers may include, but not limited to expression of CD16, CD86, CD80, CD163, CD206, CD83, CD40, CD209, HLA-DR in blister leukocytes)
 

 
To define the time course of circulating soluble and cellular inflammatory biomarker upregulation following systemic challenge with LPS or GM-CSF in healthy participants
 
	
 
Time course of regulation of circulating soluble inflammatory biomarkers (may include but is not limited to IL-1b, IL-2, IL-6, IL-8, IFN<math>\gamma</math>, TNF-<math>\alpha</math>, MCP-1, GM-CSF, CRP).
 
Time course of regulation of circulating leukocyte numbers and cellular activation markers (may include, but not limited to expression of CD16, CD86, CD80, CD163, CD206, CD83, CD40, CD209, HLA-DR in circulating leukocytes)
 

Exploratory Objectives	Exploratory Endpoints

 
To compare suitability of blisters sampled at 24 and 48 hours after induction for maximising observed effects of systemic challenge
 
	
 
Primary and Secondary endpoints measured in 24 versus 48 hour blisters
 


 
To assess the safety and tolerability profile of the challenge agents and to ensure it is not materially different from previous experience.
 
	
 
Adverse events, clinical laboratory measures, vital signs, pain scale assessments
 

 
Determining whether carboxyesterase-1 (CES-1) expression is present in monocytes following systemic GM-CSF challenge
 
	
 
Number of monocytes which are CES-1+ in blood
 

 
To compare prostaglandins in urine, blister fluid and plasma at baseline versus systemic challenge with LPS or GM-CSF
 
	
 
Quantification of prostaglandins including (but not limited to ) tetranor -PGDM, tetranor-PGEM, PGD2 and PGE2
 

 
To assess changes in whole blood transcriptome induced by systemic LPS or GM-CSF
 
	
 
Analysis of differential gene expression in whole blood taken pre-challenge and at selected times post- challenge
 

 
For LPS challenge only: to assess whether the dose of in -vivo LPS challenge is sufficient to induce innate immune tolerance
 
	
 
Quantification of inflammatory markers including (but not limited to) TNF-<math>\alpha</math> and IL-6 in blood drawn pre- and 6 hour post-systemic LPS challenge following ex vivo incubation in 'LPS-TruCulture' tubes and LPS-null TruCulture'
 

Objectives	Endpoints

 
To assess the effects of systemic LPS and GM-CSF challenges on blister healing times
 
	tubes  
 
Blister healing times (self-reported in participant diary card)
 

[1] As an exploratory endpoint, samples will be measured in the Somalogics assay. [2] Blister samples will also be used in the Somalogics assay. [3] Protein panels: IL-6, TNF- $\alpha$ (tolerized proteins), GRO-a (CXCL1) (unchanged) & IL-8 & IL-10 (hyper-responsive)	

### 2.3. Study Design

Overview of Study Design and Key Features	
Features	
 
• For Part I, a dose exploration design is used to find a dose that provides a robust inflammatory response for both LPS and GM-CSF.
 
• For Part II, an additional cohort of up to 8 participants may be enrolled if an interim analysis indicates that this would provide further precision on estimates of primary endpoints. The same 2-session design, as described above, would be used and participants will be dosed with LPS and GM-CSF at the same dose as the 8 evaluable participants from Part I.
 

Time & Events	
 
• Refer to Appendix 1: Schedule of Activities
 

Treatment Assignment	
 
• Participants will be randomised to receive either a LPS or GM-CSF in vivo challenge. The total study duration for each participant is approximately 13 weeks from screening to the final follow-up.
 

Interim Analysis	
 
• There will be ongoing data reviews conducted by the study team of any available data through the study progression.
 
• For Part I, data reviews will be performed by the study team to support whether to dose escalate to the next cohort for each challenge agent.
 
• At the end of Part 1, an interim analysis will be conducted to decide whether to enrol additional participants in Part II of the study, for the optimum dose selected in Part I.
 

## **2.4. Statistical Hypotheses / Statistical Analyses**

This is an exploratory enabling study which is primarily designed to estimate the effect of systemic exposure to LPS or GM-CSF challenge on soluble and cellular inflammatory biomarkers in blood, urine and cantharidin-induced skin blisters. There are no formal hypotheses to be tested.

### 3. PLANNED ANALYSES

Safety and biomarker data were reviewed on an ongoing basis throughout the progression of the study for dose escalation.

#### 3.1. Dose Escalation

Dose Escalation	Details
Study Review Committee (SRC)	Core GSK members included: 
 
• Study Physician Lead or their delegate; SERM; Statistician; Operations Study Lead; Epigenetics DPU, MM DPU, Scientific Operations Director, Clinical Development Manager.
 

Timing	
 
• For each challenge agent, when 2 participants were dosed (n=2 with LPS, n=2 with GM-CSF), a dose escalation meeting was held to make an assessment of tolerability and inflammatory response from Cohort 1.
 
• The dose escalation meeting was held prior to Group A in Cohort 2 being dosed with the challenge agents in Session 2.
 
• The dose escalation procedure was continued until a well-tolerated dose for LPS and GM-CSF showing a robust inflammatory response was identified.
 

Safety Data Required	
 
• Ongoing safety data was reviewed, these included:               
 
○ Participant clinical parameters (including pulse, blood pressure, respiratory rate, temperature & ECG)
 
○ Adverse events experienced by participants
 
○ A physician's clinical assessment of participant's tolerability of the prior dose of GM-CSF or LPS with presence (or absence) of symptomatic tachycardia, symptomatic hypo- or hypertension, pyrexia > 38.5c, vomiting, meningeal symptoms, rigors and any other symptoms of concern
 
○ Review of safety blood tests including FBC (and differential), U&E, CRP, LFT, glucose
 
○ Other clinical features which in the judgement of the attending physician was pertinent to dose escalation decisions
 
 
 
• Safety data was provided from PIMS (i.e. summaries and/or listings).
 

Biomarker Data Required	Primary endpoints (across all time points) were reviewed: 
 
• LPS: Circulating plasma levels of TNF-<math>\alpha</math> and IL-6 as well as urinary tetranor PGDM.
 
• GM-CSF: Circulating total leukocyte numbers.
 
 
Other available data were also reviewed to support dose escalation, but were not formally included in any dose escalation decision criteria:
 
 
• MSD & ELISA readouts from plasma, ex-vivo stimulations and blister fluid samples, Flow Cytometry readouts from blood and blister fluid / blister cell counts.
 
• Raw data for biomarkers specified were reviewed (i.e. raw data from GSK CUC
 

Dose Escalation	Details
	included: MSD/ELISA/Flow & TDL (cell counts) and raw data from GSK BIB group for urinary tetranor PGDM.)
Statistical Analyses	
 
• There were no planned formal statistical analyses of the data. Graphs were created in Excel based on the raw data obtained (nonstandard)
 

Dose Escalation Criteria	
Below is the Dose Escalation Criteria decided by the study team                      If only one participant hits stopping criteria then there will be a presumption of stopping escalation, unless in the judgement of the team further escalation would provide additional scientific value to the study without materially impacting on participant wellbeing.
 
LPS: STOP dose escalation, IF:
 
 
• Peak plasma/serum level of TNF-<math>\alpha</math> <math>\geq</math> 100 pg/mL (minimum increase of 75 pg/ml from baseline) AND
 
• Peak plasma/serum level of IL-6 <math>\geq</math> 200 pg/mL (minimum increase of 100 pg/ml from baseline) AND
 
• Urinary tetranor PGDM 3x over baseline in urine OR
 
• Presence of adverse clinical signs (fever, HR + others) which, in the opinion of the investigator, pose an unacceptable risk to participants were dose escalation to proceed. Examples may include, but are not limited to:                             
 
○ Rigors
 
○ Meningeal symptoms of moderate severity
 
○ Vomiting
 
○ Clinically significant hypotension, hypertension, tachycardia or bradycardia
 
 
 
 
GM-CSF: STOP dose escalation IF:
 
 
• Max change of circulating total leukocyte counts increase by 5 giga/L OR
 
• Presence of adverse clinical signs (fever, HR + others) which, in the opinion of the investigator, pose an unacceptable risk to participants were dose escalation to proceed. Examples may include, but are not limited to:                             
 
○ Rigors
 
○ Meningeal symptoms of moderate severity
 
○ Vomiting
 
○ Clinically significant hypotension, hypertension, tachycardia or bradycardia
 
 
 
• Elevation of platelet count above 500 x 10^9/L
 

Dose Escalation Decision	
 
• Following each dose escalation meeting, the decision to STOP or dose escalate for each challenge agent was documented,
 
• An optimum dose of 0.75 ng/kg for LPS and 60 ug/m^2 for GM-CSF was identified.
 

### 3.2. Interim Analyses

Interim Analysis	Details
Study Review Committee	Core GSK members include: 
 
• Study Physician Lead or their delegate; SERM; Statistician; Operations Study Lead; Epigenetics DPU, MM DPU, Scientific Operations Director, Clinical Development Manager.
 

Timing	
 
• At the end of Part I, an interim analysis will be conducted to decide whether to enrol additional participants in Part II of the study, for the optimum dose of 0.75 ng/kg for LPS and 60 ug / m2 for GM-CSF selected in Part I.
 

Biomarker Data Required	
 
• Data for Biomarkers listed in Section 10.3.3 will be presented in tabular and graphical format and summarized descriptively according to GSK's IDSL standards.
 

Statistical Analyses	
 
• There are no planned formal statistical analyses of the data. Descriptive summaries and/or graphical presentations will be presented, including data listings.
 

Criteria for Part II	
If at least one participant meets the criteria below for the optimal dose of 0.75ng/kg for LPS challenge or 60 ug/m2 for GM-CSF challenge, then Part II of the study will be initiated.
 
Participants will be enrolled to Part II – LPS Challenge at the dose level 0.75 ng/kg if for at least one participant:
 
 
• Maximum increase from baseline at any timepoint in plasma level of TNF-<math>\alpha</math> < 50 pg/mL AND
 
• Maximum increase from baseline at any timepoint in plasma level of IL-6 < 50 pg/mL AND
 
• Maximum increase from baseline at any timepoint in urinary tetranor PGDM level < 1.3x
 
 
Participants will be enrolled to Part II – GM-CSF Challenge at the dose level 60 ug/m2 if for at least one participant:
 
 
• Maximum increase from baseline at any timepoint in total leukocyte counts < 5 giga/L
 
• Note: Available data from all biomarkers will be considered before making the decision to move to Part II – GM-CSF Challenge.
 

Part II Decision	
 
• The decision to STOP after Part I or CONTINUE to Part II for each challenge agent will be documented, including any supporting data.
 

Biomarkers for Part II	
If a decision is made to continue to Part II of the study, then biomarkers meeting the criteria below will not be assessed in Part II.
 
 
• RNASeq and Somalogics data will not be collected for participants in Part II.
 
• If any biomarker is not detectable (< LLQ) at all timepoints for all participants
 

Interim Analysis	Details
	
of Part I at the optimal dose, the biomarker will not be assessed in Part II.
 
 
• If all analytes collected from a single sample type are not detectable (<LLQ) for all participants at all timepoints in Part I at the optimal dose, then this sample will not be collected in Part II.
 
• Additionally, the available data for all biomarkers of Part I will be reviewed to help decide if the biomarkers need to be assessed in Part II.
 

If the decision is made to Stop after Part I, then the RAP for the Final Reporting will follow and additional displays will be generated as part of the Final Reporting.

### 3.3. Final Analyses

The final planned primary analyses will be performed after the completion of the following sequential steps:

1. All participants have completed the study as defined in the protocol
2. All required database cleaning activities have been completed and final database release (DBR) and database freeze (DBF) has been declared by Data Management.
3. All criteria for releasing the randomization codes have been met (where required).
4. Randomization codes have been distributed according to RandAll NG procedures.

## 4. ANALYSIS POPULATIONS

Population	Definition /Criteria	Analyses Evaluated
Screened	
 
• All participants who were screened for eligibility
 
	
 
• Selected Study Population
 

Enrolled	
 
• All participants who passed screening and entered the study. Included are: Run-in Failures; Randomized Participants; in non-randomized study and participants who were assigned a treatment in a non-randomised study.
 
• Note screening failures (who never passed screening even if rescreened) and participants screened but never enrolled into the study (Reserve, Not Used) are excluded from the Enrolled population as they did not enter the study.
 
	
 
• Selected Study Population
 

Safety	
 
• All participants who are randomized to receive the treatment (LPS or GM-CSF challenge) and received at least one dose of challenge agent.
 
• This population will be based on the challenge agent participants actually received.
 
• Note: Participants who were not randomized but received at least one dose of challenge agent should be listed.
 
	
 
• Biomarker
 
• Safety
 

[1] Refer to [Appendix 7](#): List of Data Displays which details the population used for each display.

## 4.1. Protocol Deviations

Important protocol deviations (including deviations related to study inclusion/exclusion criteria, conduct of the trial, patient management or patient assessment) will be summarised and listed as part of the Final Reporting.

Protocol deviations will be tracked by the study team throughout the conduct of the study in accordance with the Protocol Deviation Management Plan [06Feb2018 V1.1] or higher.

- Data will be reviewed prior to unblinding and freezing the database to ensure all important deviations and deviations which may lead to exclusion from the analysis are captured and categorised on the protocol deviations dataset.
- This dataset will be the basis for the summaries and listings of protocol deviations.

A separate summary and listing of all inclusion/exclusion criteria deviations will also be provided. This summary will be based on data as recorded on the inclusion/exclusion page of the eCRF. For the Interim Analysis, no displays related to protocol deviations and inclusion/exclusion criteria deviations will be generated.

## 5. CONSIDERATIONS FOR DATA ANALYSES AND DATA HANDLING CONVENTIONS

### 5.1. Study Treatment & Sub-group Display Descriptors

Treatment Group Descriptions			
RandAll NG		Data Displays for Reporting	
Code	Description	Description	Order in TLF
A	LPS Dose 1	LPS 0.5 ng/kg	1
B	LPS Dose 2	LPS 1.0 ng/kg	3
C	LPS Dose 3	LPS 0.75 ng/kg	2
D	LPS Dose 4	LPS 0.75 ng/kg	2
G	GM-CSF Dose 1	GM-CSF 60 ug/m2	4
H	GM-CSF Dose 2	GM-CSF 60 ug/m2	4

### 5.2. Baseline Definitions

For all endpoints (except as noted in baseline definitions) the baseline value will be the latest pre-dose assessment with a non-missing value, including those from unscheduled visits. If time is not collected, Day 1 assessments are assumed to be taken prior to first dose of challenge and used as baseline.

Parameter	Study Assessments Considered as Baseline				Baseline Used in Data Display
	Screening	Session 1 Day 1	Session 1 Day 2	Session 2 Day 1	
Biomarkers					
LPS: TNF- $\alpha$ , IL6 GM-CSF: WBC (Total leukocyte counts)		X	X	X	Session 2 Day 1 (Pre Blister Induction)
Blood		X			Session 1 Day 1 (Pre Blister Induction)
Blister			X		Session 1 Day 2 (24 HR)
Urine			X		Session 1 Day 2 (Pre Fluid Sampling)
In Vivo LPS or GM-CSF				X	Session 2 Day 1 (Pre Blister Induction)
Safety					
Vital Signs & Temperature	X	X			Session 1 Day 1
ECG	X				Screening
Labs	X	X			Session 1 Day 1

Unless otherwise stated, if baseline data is missing no derivation will be performed and baseline will be set to missing.

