9.3.5. Electrocardiograms

- Triplicate 12-lead ECG will be obtained at screening and baseline as outlined in the SoA using an ECG machine that automatically calculates the heart rate and measures PR, QRS, QT, and QTc intervals. At all other time points a single ECG measurement will be taken.
- All scheduled time points for ECG measurements should be preceded by at least 5 minutes of rest for the participant in a quiet setting in a semi supine position without distractions (e.g., television, cell phones).
- At each time point at which triplicate ECG are required, 3 individual ECG tracings will be obtained as closely as possible in succession.
- Participants dosed with LPS, will receive telemetry for a minimum of 6 hours post-dose or until their telemetry shows no clinical significant findings for 4 hours (whichever is longer).
- Participants undergoing the GM-CSF challenge may be connected to continuous cardiac telemetry during their stay in the unit at the discretion of the investigator if they are symptomatic.

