#### 7.1.2. Summary Measure

Challenge	Endpoint
LPS	Absolute values and change from baseline in TNF- $\alpha$ , IL-6 and PGDM across the time course Baseline: 
 
• TNF-<math>\alpha</math>, IL-6: Session 2: Day 1 (Pre Blister Induction)
 
• PGDM: Session 1 Day 2 (Pre Fluid Sampling)
 

GM-CSF	Absolute values and change from baseline in total leukocyte across the time course 
 
• Baseline = Session 2: Day 1 (Pre Blister Induction)
 

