**10.5.3. Vital Signs**

Vital Sign Parameter (Absolute)	Units	Clinical Concern Range	
		Lower	Upper
Temperature	degrees C	<35.5	>37.5
Systolic Blood Pressure	mmHg	<85	>160
Diastolic Blood Pressure	mmHg	<45	>100
Heart Rate	bpm	<40	>110

Vital Sign Parameter (Change from Baseline)	Units	Clinical Concern Range			
		Decrease		Increase	
		Lower	Upper	Lower	Upper
Temperature	degrees C	Change of 1°C from baseline within four hours			
Systolic Blood Pressure	mmHg	≥20	≥40	≥20	≥40
Diastolic Blood Pressure	mmHg	≥10	≥20	≥10	≥20
Heart Rate	bpm	≥15	≥30	≥15	≥30

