## 10.7.4. Biomarker Tables

Biomarker Tables					
No.	Population	IDSL / Example Shell	Title	Programming Notes	Deliverable [Priority]
Soluble Inflammatory Mediators					
2.1.	Safety	BIO_T1	Summary of Primary Soluble Inflammatory Mediators in Blood	Page by Treatment and Biomarker	IA [1]
2.2.	Safety	BIO_T1	Summary of Change from Baseline in Primary Soluble Inflammatory Mediators in Blood	Page by Treatment and Biomarker.	IA [1]
2.3.	Safety	BIO_T1	Summary of Secondary Soluble Inflammatory Mediators in Blood	Page by Treatment and Biomarker	IA [1]
2.4.	Safety	BIO_T1	Summary of Change from Baseline in Secondary Soluble Inflammatory Mediators in Blood	Page by Treatment and Biomarker	IA [1]
2.5.	Safety	BIO_T1	Summary of Soluble Inflammatory Mediators from In-Vitro (un)stimulated Blood Pre and Post In-Vivo LPS Challenge	Page by Treatment and Biomarker	IA [1]
2.6.	Safety	BIO_T1	Summary of Soluble Inflammatory Mediators in Blister	Page by Treatment and Biomarker	IA [1]
2.7.	Safety	BIO_T1	Summary of Change from Baseline of Soluble Inflammatory Mediators in Blister	Page by Treatment and Biomarker	IA [1]
2.8.	Safety	BIO_T1	Summary of Soluble Inflammatory Mediators in Urine following LPS Challenge	Page by Treatment and Biomarker	IA [1]
2.9.	Safety	BIO_T1	Summary of Change from Baseline of Soluble Inflammatory Mediators in Urine following LPS Challenge	Page by Treatment and Biomarker	IA [1]
Total Leukocyte Numbers					
2.10.	Safety	BIO_T1	Summary of Cell Numbers in Blood following GM-CSF Challenge	Page by Treatment and Biomarker	IA [1]
2.11.	Safety	BIO_T1	Summary of Change from Baseline in Cell Numbers in Blood	Page by Treatment and	IA [1]

Biomarker Tables					
No.	Population	IDSL / Example Shell	Title	Programming Notes	Deliverable [Priority]
			following GM-CSF Challenge	Biomarker	
Blister Volume					
2.12.	Safety	BIO_T1	Summary of Blister Volume	Page by Treatment	IA [1]
Flow Cytometry					
2.13.	Safety	BIO_T1	Summary of Cell Activation Markers by Flow Cytometry on Monocytes in Blood	Page by Treatment and Biomarker	IA [1]
2.14.	Safety	BIO_T1	Summary of Change from Baseline in Cell Activation Markers by Flow Cytometry on Monocytes in Blood	Page by Treatment and Biomarker	IA [1]
2.15.	Safety	BIO_T1	Summary of Cell Activation Markers by Flow Cytometry on Dendritic Cells in Blood	Page by Treatment and Biomarker	IA [1]

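### Secondary blood markers are baselined to Session 1 Day 1, at least 14 days before the challenge, although a pre-challenge sample is drawn on Session 2 Day 1

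*SAP*

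**What the plan says.** SAP 5.2 opens with a default: "the baseline value will be the latest pre-dose assessment with a non-missing value". The dose meant is the challenge. A table of exceptions then overrides the default.

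- The row for TNF-α and IL-6 (LPS) and WBC (GM-CSF) uses Session 2 Day 1. SAP 7.1.2 repeats this: "TNF- \alpha , IL-6: Session 2: Day 1 (Pre Blister Induction".
- The general blood row uses "Session 1 Day 1 (Pre Blister Induction".
- A further row, 'In Vivo LPS or GM-CSF', uses Session 2 Day 1. Neither document says which parameters it covers.
- Among the safety rows, "Vital Signs & Temperature" and laboratory tests use Session 1 Day 1. ECG uses Screening ("ECG X Screening").

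The challenge is given only on Session 2 Day 1, after a healing gap of at least 14 days (Protocol 5.1). Footnotes 7 and 9 of the Schedule of Activities (Protocol 2, repeated in SAP 10.1.1) schedule a pre-challenge draw that day for mediators and for flow cytometry.

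The blood row feeds interim displays such as Table 2.4, "Summary of Change from Baseline in Secondary Soluble Inflammatory Mediators in Blood".

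**The concern.** The second secondary objective is the time course of circulating markers after the challenge. For that purpose the natural reference is the last sample before the challenge. A reference from Session 1 also captures whatever changed in the participant between sessions, including any residue of the first set of blisters.

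The SAP is also uneven. Most secondary mediators come from the same mediator sample as TNF-α and IL-6 and are run by the same method (Protocol 9.7.1.1; SAP 10.3.3), yet they get a different baseline with no reason given. Table 2.2 is paged by treatment and is not limited to LPS. Read literally, TNF-α and IL-6 therefore have a Session 2 baseline in the LPS arm and a Session 1 baseline in the GM-CSF arm.

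At stake is the reported size of the post-challenge change, with four participants per challenge at the chosen dose. The formal Part II criteria (SAP 3.2) do not use these markers. The GM-CSF decision does, however, take account of available data from all biomarkers.

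**Working it through.** **1. The plan's own figure, used here only as a yardstick.** Protocol 10.1 gives the probability of success for a true ratio of 1.4 with a 10% false-success rate. The formula Φ(ln 1.4 ÷ (SD/√n) − z₀.₉₀) reproduces it. For SD 0.394 and n = 4: 0.3365 ÷ 0.197 = 1.708; 1.708 − 1.2816 = 0.427; Φ = 66.5%.

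| SD | n = 4: stated / computed | n = 8: stated / computed |
|---|---|---|
| 0.217 | >90% / 96.6% | >90% / 99.9% |
| 0.394 | 66% / 66.5% | 87% / 87.2% |
| 0.434 | 61% / 60.6% | 82% / 81.9% |
| 0.473 | 56% / 55.6% | 77% / 76.7% |

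**2. Baseline chosen against values scheduled nearer the challenge.**

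| Parameter | SAP 5.2 baseline | Later value scheduled |
|---|---|---|
| Secondary mediators, blood | Session 1 Day 1 | Pre-challenge draw, Session 2 Day 1 |
| Flow markers and cell counts, blood | Session 1 Day 1 | Pre-challenge draw, Session 2 Day 1 |
| Vital signs | Session 1 Day 1 | Session 2 Day -1 (the Day 1 readings are set after the challenge) |
| Laboratory tests | Session 1 Day 1 | Session 2 Day -1; Day 1 timing against the challenge not stated |
| ECG | Screening | Session 2 Day -1; Day 1 timing against the challenge not stated |

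**3. Gap from Session 1 Day 1 to the challenge.** It is at least 14 days, or 14 + 2 = 16 if the healing period runs from Session 1 Day 3. No upper limit is stated for Session 2. If the four-week limit for the interim inspection applied (an assumption), the gap would be 28 + 2 = 30 days.

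**4. What the remote baseline does.** Write P(t) for a post-challenge value, B₂ for the Session 2 pre-challenge value and B₁ for Session 1 Day 1. Then

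P(t) − B₁ = [P(t) − B₂] + (B₂ − B₁).

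The last term is drift. It is one constant per participant, so it moves that participant's whole curve up or down and leaves its shape and time of peak alone. On the ratio scale, P/B₁ = (P/B₂) × (B₂/B₁).

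**5. Illustration.** The documents give no drift figure. Assume B₂/B₁ lies between 0.8 and 1.2. A true 1.4-fold rise then reads as 1.4 × 0.8 = 1.12 up to 1.4 × 1.2 = 1.68. On the yardstick in step 1 (SD 0.394, n = 4, no challenge effect), replacing ln 1.4 by ln(drift) moves the 10% false-success rate as follows:

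| Assumed drift | False-success rate |
|---|---|
| 0.8 | 0.8% |
| 0.9 | 3.5% |
| 1.1 | 21% |
| 1.2 | 36% |

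The interim analysis applies no such test, so this shows sensitivity only.

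**6. Which Session 2 sample is meant.** Cantharidin goes on 20 minutes after the end of the challenge. The schedule attaches the pre-blister-induction label to the 5-minute mediator draw, which is 20 − 5 = 15 minutes after the challenge ends. The mock shell BIO_T1 (SAP 10.8) lists a Session 2 'Pre Blister Induction' row and a separate −5 minute row. The label therefore points to two different mediator samples. Flow cytometry has no 5-minute draw.

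**The case against.** **Session 1 is the baseline session by design.** Protocol 5.1 calls it that, and the shells run both sessions in one display with one baseline footnote. This is a sound reason to keep Session 1 Day 1 for the Session 1 time course, and Session 1 for the blister comparison. It does not fit the post-challenge blood time course, and the SAP does not apply it to its own primary blood markers.

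**The 'In Vivo LPS or GM-CSF' row may already cover post-challenge blood.** The schedule uses almost the same words for the Session 2 challenge, so the reading is possible. It would, however, make the separate row for TNF-α, IL-6 and WBC redundant. Urinary tetranor PGDM staying on Session 1 settles nothing, because no pre-challenge urine is collected in Session 2. The row is ambiguous, and that itself needs repair.

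**The analysis is descriptive and drift can be seen.** This stands. Absolute values at both sessions are tabulated, plotted and listed. The change displays still carry the drift.

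A reader might also infer more than the documents support:

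- *That safety flags are distorted now.* This SAP version covers dose escalation and the interim only, SAP 8 plans no interim safety analysis, and SAP 10.7 lists no safety displays.
- *That neutrophil, lymphocyte and monocyte changes fail to add up to the WBC change because of the baselines.* The blood panel in SAP 10.3.3 lists no eosinophils or basophils, and Protocol 3.2 says GM-CSF mobilises eosinophils. The listed subsets would not sum to WBC under any shared baseline.
- *That drift eats into the 5 giga/L leukocyte criterion.* That criterion uses total WBC, which already has a Session 2 baseline.
- *That the ECG baseline is about 60 days old.* The sum 30 + 2 + 28 borrows the interim-inspection limit; the schedule sets no such limit for Session 2.

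**Conclusion.** The point holds for secondary blood mediators and blood flow-cytometry markers and, on a literal reading, for TNF-α and IL-6 in the GM-CSF arm. Their baseline precedes the challenge by at least 14 days, while a same-day pre-challenge sample exists and the default rule would choose it. The affected interim displays are Tables 2.4, 2.14, 2.16 and 2.18 and Figures 2.6, 2.8, 2.25, 2.27, 2.29, 2.31, 2.33 and 2.35. Literally read, the GM-CSF pages of Table 2.2 and Figures 2.2 and 2.4 are affected too.

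The effect is on the magnitude of change. Its size cannot be fixed from the documents; the range of 1.12 to 1.68 around 1.4 rests wholly on the assumed drift of 0.8 to 1.2.

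The vital-sign, laboratory and ECG baselines have the same weakness but drive no display here, so they matter only if carried into the final plan. For ECG there is also a mismatch with Protocol 9.3.5, which lists a baseline ECG apart from screening: "Triplicate 12-lead ECG will be obtained at screening and baseline as outlined in the SoA".

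**What to change.** In SAP 5.2:

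- For every Session 2 blood biomarker in both arms, set baseline to the Session 2 Day 1 pre-challenge draw. Use the term 'pre-challenge' in the table, in SAP 7.1.2 and in the shells. CRP comes from the laboratory dataset, so give it the last laboratory value before the challenge.
- Keep Session 1 Day 1 as the blood baseline only for the Session 1, cantharidin-only time course.
- Define the 'In Vivo LPS or GM-CSF' row or remove it.

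Before the final SAP, set the vital-sign, laboratory and ECG baselines to the last value before the challenge; Session 2 Day -1 is scheduled for all three. Reconcile the temperature flag in SAP 10.5.3, "Change of 1°C from baseline within four hours", separately. A Day -1 baseline does not satisfy it either, because no pre-challenge vital signs are scheduled on the day of the challenge.

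The cost is table wording and programming, plus a small reporting burden: change displays that span both sessions need two baselines or footnotes, and revised shells. No new data are needed.
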